## 9.2. Analysis Conventions

All individual subject data will be listed as measured. All statistical summaries and analyses will be performed using SAS® software (SAS Institute, Cary, North Carolina, USA).

### 9.2.1. Analysis Sets

#### 9.2.1.1. Pharmacokinetics (PK) Analysis Sets

##### 9.2.1.1.1. Intensive PK Analysis Set

The intensive PK analysis set will include all PK Lead-in subjects who received at least one dose of study drug and for whom at least one non-missing PK concentration data, during the intensive sampling period, reported by PK lab. The PK analysis set will be used for detailed pharmacokinetic analysis of SOF, and metabolites.

#### 9.2.1.1.2. Sparse PK Analysis Set

The PK analysis set will include all enrolled subjects who received at least one dose of study drug and for whom at least one observed concentration data of SOF or GS-331007 are available. The PK analysis set will be used for analysis of general PK and single sample plasma concentrations.

#### 9.2.1.2. Safety Analysis Set

The primary analysis set for safety analyses will include subjects who were enrolled and have received at least one dose of study drug.

Treatment-emergent data will be analyzed and defined as data collected from the first dose of study drug through the date of last dose of study drug plus 30 days.

#### 9.2.1.3. Efficacy Analysis Set

The analysis set for antiviral activity analyses will be the Full Analysis Set (FAS) which includes HCV infected subjects who were enrolled and have received at least one dose of study drug.

### 9.2.2. Data Handling Conventions

Natural logarithm transformation for key PK parameters, such as  $C_{max}$  and  $AUC_{tau}$ , will be applied for pharmacokinetic analysis.

The PK concentration values below the limit of quantitation (BLQ) will be treated as zero for the determination of summary and order statistics. Individual values that are BLQ will be presented as “BLQ” in the concentration data listing and will be excluded in any calculation of geometric means or ratios. For the presentation of summary and order statistics, if at least 1 subject has a concentration value BLQ for the time point, then the minimum value will be displayed as “BLQ”. If more than 50% of the subjects have a concentration data value BLQ for the time point, then the minimum and median values will be displayed as “BLQ”. If all subjects have concentration data values BLQ for the time point, then all order statistics (minimum, first quartile [Q1], median, third quartile [Q3], maximum) will be displayed as “BLQ”.

Missing data can have an impact upon the interpretation of the trial data. Other than the endpoints discussed below, in general, values for missing data will not be imputed.

For the analysis of post-baseline categorical efficacy endpoints, if a data point is missing and is preceded and followed in time by values that are deemed successes, then the missing data point will be termed a success; otherwise the data point will be termed a failure.

Any subject with missing data due to premature discontinuation of the study medication will be considered a failure at the time points subsequent to the date of discontinuation. If no HCV RNA values are obtained after the last dose of study medication, the subject will be considered a treatment failure for the SVR endpoints.

Where appropriate, safety data for subjects that did not complete the study will be included in summary statistics. For example,

- If a subject received study medication, the subject will be included in a summary of adverse events according to the treatment received; otherwise, if the subject is not dosed then they will be excluded from the summary.
- If safety laboratory results for a subject are missing for any reason at a time point, the subject will be excluded from the calculation of summary statistics for that time point. If the subject is missing a pre-dose value, then the subject will be excluded from the calculation of summary statistics for the pre-dose value and the change from pre-dose values.

Values for missing safety laboratory data will not be imputed; however, a missing baseline result will be replaced with a screening result, if available. If no pre-treatment laboratory value is available, the baseline value will be assumed to be normal (i.e., no grade [Grade 0]) for the summary of graded laboratory abnormalities.

Values for missing vital signs data will not be imputed; however, a missing baseline result will be replaced with a screening result, if available.

HCV RNA values below the LLOQ for the assay will be set to the lower limit minus 1 for calculation of summary statistics for the actual HCV RNA values and the change from baseline values by study visit. The reported values will be provided in the HCV RNA listing.

For selected analyses of early time point data, HCV RNA data (IU/mL) may be transformed to the logarithmic (base 10) scale ( $\log_{10}$  IU/mL).

### **9.2.3. Interim Analysis**

No formal interim analyses are planned for this study.

### **9.3. Demographic Data and Baseline Characteristics**

Demographic and baseline measurements will be summarized using standard descriptive methods by age group and overall for PK Lead-in and Treatment Phase respectively.

Demographic data will include sex, self-identified race/ethnicity, and age.

Baseline characteristic data will include body weight, height, body mass index, HCV RNA level ( $\log_{10}$  IU/mL), HCV GT, prior treatment experience, and additional endpoints as necessary.

### **9.4. Pharmacokinetic Analysis**

PK analysis will be performed for PK Lead-in using the intensive PK analysis set. The concentration data of SOF and metabolites (GS-566500 and GS-331007) over sampling time will be listed and summarized by nominal time and cohort. Pharmacokinetic parameters (e.g.,  $AUC_{\tau}$ ,  $AUC_{last}$ ,  $C_{max}$ ,  $T_{max}$ ,  $C_{last}$ ,  $T_{last}$ ,  $C_{\tau}$ ,  $\lambda_z$ ,  $CL/F$ ,  $V_z/F$  and  $t_{1/2}$ ) will be listed and

summarized for SOF and metabolites (as applicable) using descriptive statistics (e.g., sample size, arithmetic mean, geometric mean and its 95% confidence interval, coefficient of variation %, standard deviation, median, Q1, Q3, minimum, and maximum) by cohort and overall. Plasma concentrations over time will be plotted in semilogarithmic and linear formats as mean  $\pm$  standard deviation, and median (Q1, Q3).

To evaluate the exposures of GS-331007 achieved in pediatric subjects of this study are similar to the exposures observed in adult subjects, GS-331007 exposure data from this study will be compared to the integrated adult data by carrying out an analysis of variance (ANOVA) for log-transformed  $AUC_{\tau}$  of GS-331007 as the primary endpoint while  $C_{\max}$  of GS-331007 as secondary endpoints. The 90% confidence intervals will be constructed for the ratio of geometric means of each PK parameters. The equivalence boundary is set as 50% to 200%. Individual patient management will be performed by maintaining exposures comparable to adults.  $AUC_{\tau}$  less than the 2.5th percentile of adult values may require dose adjustment as appropriate.

The effect of age and SOF dose on PK (SOF and GS-331007) will be assessed.

## **9.5. Safety Analysis**

Safety analysis will be performed for PK Lead-in and overall study Treatment Phases respectively. Safety data will be summarized by age group, by GT, by overall and by age group and GT.

Safety will be evaluated by assessment of clinical laboratory tests, physical examinations, vital signs measurements, and by the documentation of AEs.

All safety data collected while on or after the first dose of study drug administration up to 30 days after the last dose of study drug will be summarized by cohort according to the study drug received.

Safety endpoints will be analyzed by the number and percent of subjects with events or abnormalities for categorical values or 8-number summary (n, mean, standard deviation, median, Q1, Q3, minimum, maximum) for continuous data.

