## **9. STATISTICAL CONSIDERATIONS**

### **9.1. Analysis Objectives and Endpoints**

#### **9.1.1. Analysis Objectives**

The primary objective of PK Lead-in Phase of this study is:

- To evaluate the steady state pharmacokinetics (PK) and confirm the dose of SOF in HCV-infected pediatric subjects

The secondary objective of PK Lead-in of this study is:

- To evaluate the safety and tolerability of 7 days of dosing of SOF + RBV in HCV-infected pediatric subjects

The primary objective of Treatment Phase of this study is:

- To evaluate the safety and tolerability of SOF + RBV for 12 or 24 weeks in HCV-infected pediatric subjects with GT-2 or GT-3, respectively

The secondary objectives of Treatment Phase of this study are:

- To determine the antiviral efficacy of SOF + RBV treatment in GT-2 and GT-3 HCV-infected subjects separately, as assessed by the proportion of subjects with SVR 12 weeks after completion of treatment (SVR12)
- To determine the antiviral efficacy of SOF + RBV treatment in GT-2 and GT-3 HCV-infected subjects separately, as assessed by the proportion of subjects with SVR 4 and 24 weeks after completion of treatment (SVR4 and SVR24)
- To evaluate the kinetics of circulating HCV RNA during treatment and after completion of treatment
- To evaluate the emergence of viral resistance to SOF during treatment and after completion of treatment
- To evaluate the palatability of SOF oral granules at Day 1, as applicable.
- To evaluate the effect of growth and development of pediatric subjects during and after treatment.

The exploratory objective of this study is:

- PPD [REDACTED]

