### 9.1.3. Secondary Endpoints

For the PK Lead-in Phase, the secondary endpoints include antiviral activity measurements, including assessment of HCV RNA. AEs leading to permanent discontinuation of study drug(s) will be evaluated as a secondary safety endpoint.

For Treatment Phase, secondary efficacy endpoints include SVR4, SVR24, breakthrough and relapse. Additional efficacy evaluations may include HCV RNA change from Day 1; ALT normalization; viral kinetic parameters, and palatability of SOF oral granules. Secondary safety endpoints of growth and development measurements will be assessed (e.g. height, weight, and Tanner Stage Assessment).

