### **9.6. Efficacy Analysis**

Efficacy will be evaluated using scheduled assessments of HCV RNA performed using COBAS® TaqMan® HCV Test, v2.0 for use with the High Pure System.

Efficacy analysis will be performed by age group, by GT, by overall, and by age group and GT for Treatment Phase.

All continuous endpoints will be summarized using an 8-number summary (n, mean, standard deviation, median, Q1, Q3, minimum, maximum). All categorical endpoints will be summarized by number and percentage of subjects who meet the endpoint definition.

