1.1. Study Objectives

The primary objectives of this study are as follows:

- The primary objective of the pharmacokinetics (PK) Lead-in Phase of this study is to evaluate the steady state PK and confirm the dose of sofosbuvir (SOF) in hepatitis C virus (HCV)-infected pediatric subjects.
- The primary objective of the Treatment Phase of this study is to evaluate the safety and tolerability of SOF + ribavirin (RBV) for 12 or 24 weeks in HCV-infected pediatric subjects with genotype 2 or 3, respectively

The secondary objectives of this study are as follows:

- The secondary objective of the PK Lead-in Phase of this study is to evaluate the safety and tolerability of 7 days of dosing of SOF + RBV in HCV-infected pediatric subjects.
- The secondary objectives of the Treatment Phase of this study are:
 - To determine the antiviral efficacy of SOF + RBV treatment in genotypes 2 and 3 HCV-infected subjects separately, as assessed by the proportion of subjects with sustained viral response 12 weeks after discontinuation of therapy (SVR12)
 - To determine the antiviral efficacy of SOF + RBV treatment in genotypes 2 and 3 HCV-infected subjects separately, as assessed by the proportion of subjects with sustained viral response 4 and 24 weeks after discontinuation of therapy (SVR4 and SVR24)
 - To evaluate the kinetics of circulating HCV RNA during treatment and after treatment discontinuation
 - To evaluate the emergence of viral resistance to SOF during treatment and after treatment discontinuation
 - To evaluate the palatability of SOF oral granules at Day 1, as applicable
 - To evaluate the effect of growth and development on pediatric subjects during and after treatment

The exploratory study objective is as follows:

- PPD

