3.2. Subject Grouping

For analyses based on the All Enrolled Analysis Set or FAS, subjects will be grouped according to the treatment to which they were enrolled. For analyses based on the Safety Analysis Set, subjects will be grouped according to the actual treatment received. The actual treatment received is defined as the enrolled treatment except for subjects who received treatment that differs from the enrolled treatment for the entire treatment duration. In this case, the actual treatment received is defined as the treatment received for the entire treatment duration.

Specifically, efficacy and safety analyses will be performed according to age group and HCV genotype in the following treatment groups:

Table 3-1. Treatment Groups

12 to < 18 Years Old SOF(400mg)+RBV		3 to < 12 Years Old SOF(200mg or 150mg)+RBV	
GT-2 12 Weeks (N =)	GT-3 24 Weeks (N =)	GT-2 12 Weeks (N =)	GT-3 24 Weeks (N =)
6 to < 12 Years Old SOF(200mg)+RBV		3 to < 6 Years Old SOF(200mg or 150mg)+RBV	
GT-2 12 Weeks (N =)	GT-3 24 Weeks (N =)	GT-2 12 Weeks (N =)	GT-3 24 Weeks (N =)

GT = genotype

Subjects in the 3 to < 6 years of age group will have additional selected efficacy and safety analyses performed according to baseline weight and HCV genotype in the following subgroups:

Table 3-2. Subgroups for Selected Analyses in 3 to < 6 years of Age

3 to < 6 Years Old			
GT-2 12 Weeks		GT-3 24 Weeks	
< 17 kg SOF(150mg)+RBV (N =)	>= 17 kg SOF(200mg)+RBV (N =)	< 17 kg SOF(150mg)+RBV (N =)	>= 17 kg SOF(200mg)+RBV (N =)

GT = genotype

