7.11. Changes From Protocol-Specified Safety Analyses

There are no deviations from the protocol-specified safety analyses.

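### The SAP specifies no PK Lead-in safety summary, although Protocol 9.5 requires one, and SAP 7.11 wrongly reports no deviation; the Lead-in HCV RNA endpoint also has no summary of its own

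*Protocol*

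**What the plan says.** **Objective.** Protocol 9.1.1 gives the PK Lead-in one secondary objective: "To evaluate the safety and tolerability of 7 days of dosing of SOF + RBV in HCV-infected pediatric subjects". SAP 1.1 repeats it: "The secondary objective of the PK Lead-in Phase of this study is to evaluate the safety and tolerability of 7 days of dosing".

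**Endpoints.** Protocol 9.1.3 names two kinds of Lead-in secondary endpoint. The first is virological: "For the PK Lead-in Phase, the secondary endpoints include antiviral activity measurements, including assessment of HCV RNA". The second is a safety endpoint: "AEs leading to permanent discontinuation of study drug(s) will be evaluated as a secondary safety endpoint".

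**Analyses the protocol requires.** Protocol 9.5 says "Safety analysis will be performed for PK Lead-in and overall study Treatment Phases respectively". For efficacy, Protocol 9.6 gives methods for one phase only: "Efficacy analysis will be performed by age group, by GT, by overall, and by age group and GT for Treatment Phase".

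**Analyses the SAP provides.** SAP 3.2 sets the structure for Sections 6 and 7: "Specifically, efficacy and safety analyses will be performed according to age group and HCV genotype in the following treatment groups". Adverse event tables (SAP 7.1.6) follow those groups in the Safety Analysis Set. The treatment-emergent period (SAP 7.1.5.1) runs from the start of study drug to 30 days after its permanent discontinuation. The only analysis set and analysis specific to the Lead-in are for pharmacokinetics (SAP 3.1.4 and 8.1).

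**Declared changes.** SAP 7.11, on safety, reads "There are no deviations from the protocol-specified safety analyses". SAP 6.4, on efficacy, records only the move to sequential testing of SVR12.

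**The concern.** A protocol that separates its safety analysis into two phases, and gives the first phase its own safety objective, needs an output that answers that objective. If the SAP is followed exactly, no such table is produced. The age-by-genotype columns mix Lead-in subjects with those enrolled later, and they cover 12 or 24 weeks of treatment plus 30 days. The two sets of subjects also differ: Lead-in subjects had to be treatment-naive, and Cohorts 1 and 2 had weight limits (Protocol 4.2). A reader of the study report could not extract a seven-day safety result by cohort from those columns.

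The second problem is the record of changes. SAP 7.11 tells the reader that nothing in the protocol's safety plan was altered, when one required component is absent.

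The antiviral side is similar but weaker. A Lead-in endpoint is named in Protocol 9.1.3, and neither an analysis nor a note of its omission appears in the SAP.

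**Working it through.** There is no figure in the plan to reproduce. The check compares the passages and applies the visit-window rules by hand.

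**1. Safety: required against planned.**

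| Item | Protocol | SAP |
|---|---|---|
| Lead-in safety objective | 9.1.1, stated | 1.1, restated |
| Lead-in safety endpoint | 9.1.3, adverse events leading to permanent discontinuation | No Lead-in table; tabulated only for the full treatment groups (7.1.6) |
| Safety analysis by phase | 9.5, Lead-in and Treatment Phase | No Lead-in population or period in Sections 3 or 7 |
| Change recorded | n/a | 7.11, none |

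The two-phase structure in the protocol looks deliberate, since Protocol 9.3 asks for demographic and baseline summaries by phase as well. The only separate plan that the SAP cites is the one for the adolescent SVR12 analysis (SAP 6.1.3 and 6.4), so no other cited plan fills the gap.

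**2. Antiviral activity.** Protocol 9.1.3 names HCV RNA as a Lead-in endpoint. Protocol 9.6 gives no Lead-in method. SAP 6.2.2 has no Lead-in summary, and SAP 6.4 does not mention it.

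**3. What happens to Lead-in Day 3 and Day 7 records.** Inputs: SAP Table 3-3 sets the Week 1 window at days 2 to 11, with nominal day 7. SAP 3.7.2 takes Week 1 for Lead-in subjects from the Lead-in Day 7 visit. SAP 3.7.3 keeps the record closest to the nominal day and, in a tie, the later one. Protocol 6.3.3 allows the Day 7 visit to fall up to 3 days late, and as late as Day 11 after non-compliant dosing.

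- Day 3 distance from nominal: |3 − 7| = 4.
- Day 7 visit held on Day 7: |7 − 7| = 0, so it is kept.
- Day 7 visit held on Day 10: |10 − 7| = 3, so it is kept.
- Day 7 visit held on Day 11: |11 − 7| = 4, a tie with Day 3, so the later record is kept.

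Whenever a Day 7 record exists, Day 3 HCV RNA and laboratory values therefore drop out of the by-visit summaries. The Day 7 values are pooled into Week 1 with subjects who were never in the Lead-in.

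**4. Where Day 3 laboratory values still count.** The single-record rule applies only where one value per window is needed. Treatment-emergent abnormalities (SAP 7.2.2.1) use any postbaseline time point, the abnormality tables (7.2.2.2) use the worst postbaseline grade, and liver-related events (7.2.2.3) use all on-treatment postbaseline visits. Day 3 values enter all of these, and the by-subject listings.

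**5. Size.** Planned Lead-in: 3 cohorts × up to 10 = up to 30 of about 100 subjects. Protocol 1.2.1.4 reports 10 in Cohort 1 and 12 in Cohort 2, so with up to 10 in Cohort 3 the total could be 10 + 12 + 10 = 32.

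**The case against.** The strongest reply is that these subjects are analysed, only not separately. Adverse events leading to discontinuation are tabulated overall and by drug. Exposure is counted through Day 7 (SAP 4.2.1). Lead-in Day 7 values are mapped to Week 1 on purpose. The age groups in SAP Table 3-1 match the cohorts' age bands. Protocol 9.5 also sets no Day 7 cut-off of its own: it summarises safety from first dose to 30 days after the last, and dosing continues without a break. The Lead-in's practical purpose, dose confirmation, is served by a PK and safety review of each cohort, and Protocol 1.2.1.4 already describes preliminary safety for Cohorts 1 and 2. A data monitoring committee also reviews safety.

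Most of this stands, and it limits the consequence. It does not supply the missing analysis. Pooled tables over 12 or 24 weeks do not answer a seven-day question, and the account in Protocol 1.2.1.4 is brief, preliminary and has nothing on Cohort 3. The seven-day limit comes from the stated objective, even though Protocol 9.5 does not say how Lead-in events are to be separated.

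Three stronger readings are tempting, and the documents do not support them:

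- A reader might infer that Day 3 results are used nowhere. Only the by-visit summaries lose them. Day 3 laboratory values enter the worst-grade and liver-event tables, and Day 3 data are listed.
- A reader might take antiviral activity to be the Lead-in's secondary objective. It is an endpoint under Protocol 9.1.3; the objective is safety and tolerability only.
- A reader might charge SAP 7.11 with hiding the antiviral omission. That section covers safety alone; the place for the antiviral omission is SAP 6.4. Since Protocol 9.6 specifies no Lead-in efficacy method, the SAP dropped no stated method there. It left a named endpoint without one.

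**Conclusion.** SAP 7.11 is wrong as written when set against Protocol 9.5. The protocol requires a Lead-in safety analysis, the SAP specifies none, and the Lead-in's only secondary objective is left without a dedicated summary. The antiviral gap is real but rests on Protocol 9.1.3 alone. Severity is minor: about 30 subjects are concerned, the missing outputs are descriptive, and no primary inference depends on them.

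The conclusion assumes that the word respectively in Protocol 9.5 means a separate analysis for each phase, which the parallel wording in Protocol 9.3 supports. It also assumes that no plan outside these documents covers Lead-in safety. It does not follow that Lead-in data are lost, or that doses were confirmed without looking at safety; the protocol provides for that review.

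**What to change.** **Safety.** Add to SAP Section 7 a descriptive summary by cohort, restricted to Lead-in subjects and to the period from first dose through the actual Day 7 intensive PK visit. It should cover treatment-emergent adverse events, adverse events leading to permanent discontinuation, and graded laboratory abnormalities. The period should follow the actual visit, because that visit may fall as late as Day 11 and a fixed cut at day 7 would truncate the data. State how the period ends for a subject who stops treatment before that visit.

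**Antiviral activity.** Add to SAP 6.2.2 a by-cohort summary of HCV RNA change from baseline at Day 3 and Day 7 for Lead-in subjects, with a separate Day 3 window so that those values are not displaced by Day 7.

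**If either is left out on purpose.** Correct SAP 7.11 for safety and SAP 6.4 for antiviral activity, so that each records the omission and gives a reason.

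**Cost.** A few extra descriptive tables on about 30 subjects, from data already scheduled for collection. The note-only alternative costs a sentence in each section but leaves the Lead-in objective without its own result.

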### **9.5.1. Extent of Exposure**

A subject's extent of exposure to study drug will be generated from the study drug administration page of the CRF. Exposure data will be summarized.

